# Statistical Analysis Plan

GlaxoSmithKline

Study alias & e-track number(s): ZOSTER-063 (204928)

**Figure 1 Hypothetical Example of utility Scores over Time**

**Table 5 Calculation of QALY for hypothetical Subject in figure 1**

Day	Score	$t_{k+1}-t_k$	$(Y_k+Y_{k+1})/2$	Product
-7	0.89			
0	0.85	1	0.800	0.800
1	0.75	1	0.725	0.725
2	0.70	1	0.710	0.710
3	0.72	1	0.730	0.730
4	0.74	1	0.745	0.745
5	0.75	1	0.765	0.765
7	0.78	2		
8	0.8			
Total				4.475

Note. The value at day 7 is interpolated from the values at day 5 and day 8.

The baseline score is calculated as  $7*(0.89+0.85)/2 = 6.09$

The AUC between days 0 and 7 is 4.475. Hence the QALY loss / week is calculated as 1.534.

The 95% CI for the LSmeans of the QALY loss will be obtained using a multiple regression model. The model will include age strata, gender and frailty status as the fixed effect. The Following Code will implement this model in SAS:

```
ods output lsmeans=lsmeans;
proc mixed data=DATASET;
  class agecat gender frail;
  model qaly=agecat frail gender/ cl;
  lsmeans frail/pdiff cl;
  lsmeans gender/pdiff cl;
  lsmeans agecat/pdiff cl;
quit;
run;
```

The 95% CI for utility scores will be obtained pre- and post-vaccination separately assuming that utility scores were normally distributed with unknown variance.

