1.2. Rationale for the study and study design

1.2.1. Rationale for the study

Nearly 22,900 subjects received the active HZ/su study vaccine in clinical trials worldwide, most of whom (95%) were ≥ 50 YOA. Due to the high efficacy of the vaccine, most HZ and PHN cases were prevented, thus avoiding any negative impact on QoL in those subjects. No imbalance between the vaccine and the placebo arms were found in terms of SAEs, potential Immune-Mediated Diseases (pIMDs) or death during the entire duration of the studies. The vaccine was generally well tolerated. However, the vaccine was more reactogenic than placebo (saline solution).

In the pooled analysis of the ZOSTER-006 and ZOSTER-022 studies the most common side effects were at the site of injection, including pain, redness, and swelling. Up to 70% of people who received the HZ/su vaccine had pain at the injection site. These symptoms were usually mild and resolved within about 3 days on average. The incidence of grade 3 solicited local pain, was about 4%, with an average duration of less than 2 days. Grade 3 reactogenicity is defined as preventing ADL. Other side effects seen in more than 10% of people who received the vaccine included myalgia, fatigue, headache, shivering, fever

and gastrointestinal symptoms such as nausea, vomiting, diarrhoea and/or abdominal pain. The incidence of myalgia and fatigue was about 33% (overall/dose) and had an average duration of 2.5 days. The incidence of grade 3 solicited general symptoms was 3% or less (overall/dose) with average durations of less than 2 days. The reactogenicity is likely to be secondary to the enhanced innate immune responses elicited at the site of injection and therefore is expected [Didierlaurent, 2014]. This is consistently observed in studies evaluating AS01 – (and other) adjuvanted vaccines, in which higher reactogenicity is observed with adjuvanted versus non-adjuvanted vaccines [Stassijns, 2016].

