5.5.2.3. Review and transcribe pre-vaccination diary cards

The investigator/study staff will ensure that subject has completed the (Visit 2) pre-vaccination diary cards prior to Vaccination 1. The investigator or designee will transcribe the information that the subject documented on the diary card prior to the visit into the eCRF.

5.5.2.4. Distribution and completion of SF-36 and EQ-5D questionnaires at Visit 2

The SF-36 and EQ-5D questionnaires will be distributed to subjects again at Visit 2. Subjects will be asked to complete the entire SF-36 and EQ-5D questionnaires on site just before vaccination at Visit 2. Completed questionnaires will then be collected and subject responses will be transcribed into the e-CRF. The same procedure for questionnaires will be followed at Visit 4 (see Section [5.5.2.11](#)).

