### 6.2.1. SF-36 and EQ-5D

The SF-36 health survey and the EQ-5D questionnaires will be completed by all subjects at each study visits (i.e., Visit 1 Day -7, Visit 2 Month 0 (before the vaccination), Visit 3 Day 7, Visit 4 Month 2 (before the vaccination) and Visit 5 Day 67). Additionally, after each vaccination, the subjects will be given the questionnaires to take home and asked to complete only questions 3a through 3j of the SF-36 questionnaires and the entire EQ-5D questionnaires, on a daily basis on Days 1 to 6 post-vaccination.

Each of the 8 components of the SF-36 Questionnaire and the EQ-5D Utility and VAS scores will be presented at each scheduled visit (Day -7, Day 0, Day 7, Day 60 and Day 67) including the derived baseline values for each dose. In addition the SF-36 physical functioning score (PF) (based on questions 3a to 3j) and the EQ-5D utility and VAS scores will be presented on days 1 to 6 following each dose. Further details of the SF-36 components and EQ-5D Utility and VAS scores can be found in section [7.1.3](#).

The primary endpoint variable is the SF-36 Physical Functioning (PF) scale. The analysis will be performed on the subgroups detailed in [Table 1](#).

The 10 individual questions that form the SF-36 PF scale will be analysed on an individual basis. The three responses (Limited a lot, Limited a little, Not limited at all) to the individual questions will be assigned a score of 0, 50, or 100. In this way a baseline score and a mean score over the 7 days post each dose can be calculated for each individual question. Summary statistics of the change from baseline will be presented for each individual question.

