### Step3

The QALY Loss is then calculated as the difference between the baseline utility (from step 1) and the AUC value (from step 2).

It is anticipated that the majority of subjects will have daily assessments post dose according to the schedule (i.e. on each of the days 1 to 7) however it is expected that some subjects will be missing daily assessments post dose. In the case of missing assessments between days 1 and 7 the AUC in step 2 will be calculated regardless of the number of assessments post dose. However in the case of the last assessment falling outside of the 7 day window, (for example on day 8), an adjustment will be made before calculating the AUC.

[Figure 1](#) represents the Utility scores for a hypothetical subject. This subject has consecutive assessments on day 5 and day 8 and no assessments on days 6 or 7. Because the AUC must be calculated over a period of 7 days, the day 8 value cannot be included in the formula. However to calculate the AUC, a derived value on day 7 is calculated based on a linear interpolation of the values on days 5 and 8. This derived value on day 7 is then included in the formula given in step 2. The dashed line in the figure represents the linear interpolation between the two assessments either side of day 7.

The calculation of the QALY loss for this hypothetical subject is explained in [Table 5](#).

[figure not shown]

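### When early EQ-5D forms are missing, the SAP's QALY area bridges the reaction days from the pre-vaccination score and understates that subject's loss

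*SAP*

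**What the plan says.** QALY loss is a per-subject figure: seven times the mean pre-vaccination utility, minus a trapezoidal area over the week after the dose (SAP 7.1.3.4, Steps 1 to 3). On missing days, Step 3 says that "the AUC in step 2 will be calculated regardless of the number of assessments post dose". It interpolates only where the last form falls after Day 7. SAP 7.2.3 deals with missing baseline forms and gives no rule for a missing Day 1, 2 or 3.

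The worked example (Table 5) takes the baseline as "7*(0.89+0.85)/2 = 6.09" and opens the area with the Day 0 row, "0 0.85 1 0.800 0.800". It concludes: "The AUC between days 0 and 7 is 4.475". The Day 0 form precedes the dose: "Subjects will be asked to complete the entire SF-36 and EQ-5D questionnaires on site just before vaccination at Visit 2" (Protocol 5.5.2.4). Days 1 to 6 are home forms and Day 7 is completed on site, so a subject with no home forms can still have an end point.

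The start day is not stated consistently. Protocol 10.5 sums from 0. The Step 2 symbol is labelled 0-7 and Table 5 starts at Day 0. But the opening of SAP 7.1.3.4 gives the period as Days 1 to 7, and the Step 2 sum runs from k = 1 to 6 with the score indexed by day.

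SAP 6.2.3 adds a sensitivity analysis of QALY loss restricted to subjects with valid forms on at least 4 of the 7 days.

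**The concern.** A trapezoid joins neighbouring observed points. If the area starts at Day 0 and the first home forms are missing, the line runs from a score taken before any reaction to the first score available afterwards. The documents expect short reactions: myalgia and fatigue "had an average duration of 2.5 days" (Protocol 1.2.1). The days filled in this way are therefore those on which most of the loss is expected, and the subject enters the main QALY model like any other. This happens for such a record even if its forms were lost completely at random.

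QALY change after each dose is a secondary endpoint. It is meant to feed cost-effectiveness models and to be set against the loss from herpes zoster (Protocol 1.2.1 and 1.2.2).

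**Working it through.** **Inputs (SAP Table 5).** Baseline mean (0.89 + 0.85)/2 = 0.87, times 7 = 6.09. Scores: Day 0 0.85; Day 1 0.75; Day 2 0.70; Day 3 0.72; Day 4 0.74; Day 5 0.75; Day 7 0.78 (interpolated from Days 5 and 8).

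**The plan's own figure.** The printed products add to 0.800 + 0.725 + 0.710 + 0.730 + 0.745 + 0.765 = 4.475. The last row, "5 0.75 1 0.765 0.765", gives width 1 to the interval from Day 5 to Day 7, which is two days long. With the true width the last product is 2 x 0.765 = 1.530, the area is 5.240, and the loss is 6.09 - 5.240 = 0.850. The printed loss of 1.534 follows from neither area, since 6.09 - 4.475 = 1.615.

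**Removing early forms (Day 0 start, true widths).** The missing stretch is replaced by its length times the mean of Day 0 and the next score.

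| Forms missing | Bridge | Area | Loss | Change from 0.850 |
|---|---|---|---|---|
| As in Table 5 | - | 5.240 | 0.850 | - |
| Day 1 | 2 x (0.85+0.70)/2 = 1.550 | 5.265 | 0.825 | -3% |
| Days 1-2 | 3 x (0.85+0.72)/2 = 2.355 | 5.360 | 0.730 | -14% |
| Days 1-3 | 4 x (0.85+0.74)/2 = 3.180 | 5.455 | 0.635 | -25% |
| All but Day 7 | 7 x (0.85+0.78)/2 = 5.705 | 5.705 | 0.385 | -55% |

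The last row treats 0.78 as an observed Day 7 score.

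**When the loss reaches zero.** Assume a baseline and Day 0 of 0.87, a flat drop d on Days 1-3, and full recovery from Day 4. The full-data loss is 3d: 0.30, 0.60 and 0.90 for d = 0.1, 0.2 and 0.3. Without Day 1 it is 2.5d, without Days 1-2 it is 2d, and without Days 1-3 (or all home forms) it is 0. The drops are illustrative and are not document figures.

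**The opposite error.** If the Table 5 subject has Days 1-3 and nothing later, the area stops at 0.800 + 0.725 + 0.710 = 2.235 and the loss is 6.09 - 2.235 = 3.855, which is 3.005 too high. A Day-7-only record is 0.850 - 0.385 = 0.465 too low. One such early-ending record thus offsets about 3.005/0.465 = 6.5 Day-7-only records.

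**Day 1 start instead.** The Table 5 subject's area is 5.240 - 0.800 = 4.440 and the loss 1.650. Without Days 1-3 the area is 0.745 + 1.530 = 2.275 and the loss 3.815, so missing early forms now raise the loss. This reading sets six days of area against seven of baseline: a constant 0.87 gives 6.09 - 6 x 0.87 = 0.87 of loss with no change in health.

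**The 4-of-7 restriction.** It drops the Day-7-only record. It keeps a subject with forms on Days 4, 5, 6 and 7 alone, who in the assumed profile scores 0.

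**The case against.** The strongest objection is that the Day 0 start is only one of two readings. The text and the Step 2 limits can be taken as a Day 1 start, under which the bias reverses. That stands as an inconsistency to be settled. The Day 0 start is still the only coherent reading: Step 3 requires an area over seven days, the baseline is multiplied by seven, the symbol is labelled 0-7, the protocol sums from 0, and the only worked example starts there.

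Three stronger conclusions are tempting, and the documents do not support them.

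- A reader might infer that the mean QALY loss is pulled toward zero. That is not shown. The same rule overstates the loss where no form on Day 7 or later exists, and no missing-form rate is given. Step 3 also expects most subjects to have daily forms.
- A reader might infer that a subject with no home forms is scored as having no loss. That needs recovery by the first available form and a Day 0 score equal to the baseline mean. The SAP's own subject scores 0.385.
- A reader might take the 4.475 as showing the understatement. It shows the reverse: the two-day gap is given one day of area, which inflates the loss.

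It is also fair that the analyses are descriptive (Protocol 10.7), that compliance is tabulated by time point (SAP 6.2.1.1), and that the 4-of-7 analysis covers QALY loss. These limit the consequence but leave the main analysis unchanged.

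**Conclusion.** The point holds for individual records, on the Day 0 reading with true widths. A subject missing early home forms but with a form on Day 7 or later has the loss understated: by 3% to 25% for the SAP's example subject when one to three early days are missing, by 55% with Day 7 only, and by up to 100% under the assumed recovery by Day 4. Records that end early are overstated by the same rule. The net effect on the mean therefore cannot be signed or sized from the documents. The existing safeguard is a sensitivity analysis that does not require an early day. This is a cheap improvement to a secondary endpoint and does not touch the primary SF-36 analysis.

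**What to change.** 1. Reconcile Protocol 10.5, the opening text of SAP 7.1.3.4, the Step 2 formula and Table 5 on the start day and on the width given to gaps. Correct Table 5 to an area of 5.240 and a loss of 0.850.
2. For the main QALY analysis, take the daily loss (mean baseline utility minus that day's utility) on Days 1-7 as a repeated measure, with day as a factor and the planned age, gender and frailty terms. Report the sum of the seven day-specific means with its 95% CI. State how site forms dated Days 8-10 are assigned, since the visit window in Protocol Table 6 allows them.
3. If a per-subject area is kept, do not let the pre-vaccination score fill missing Days 1-6. Multiply impute those days from the subject's other EQ-5D days and the diary grades.
4. Show the bridged area as a sensitivity analysis.

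No new data are needed. The cost is SAP wording, some programming, a missing-at-random assumption and a slightly wider interval. The sum of seven daily losses is also not identical to the trapezoid, which gives half weight to Days 0 and 7. The difference is half of (Day 7 loss minus Day 0 loss), or (0.09 - 0.02)/2 = 0.035 for the Table 5 subject, and the SAP should say which quantity is reported.

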2.2. Secondary objectives

[figure not shown]
- To estimate the change in the SF-36 PF scale score from baseline score to the mean score over the period day 1 to day 7 following the second HZ/su vaccination in subjects ≥ 50 YOA overall.
- To estimate the change in the SF-36 PF scale score in subjects ≥ 50 YOA by age, gender and reactogenicity grade and type of symptom (local, systemic) from baseline score to the mean score over the period day 1 to day 7 following both HZ/su vaccinations 1 and 2.
- To estimate the change in SF-36 PF single item scores in subjects ≥ 50 YOA overall, by age, gender and reactogenicity grade and type of symptom (local, systemic) from baseline score to the mean score over the period day 1 to day 7 following both HZ/su vaccinations 1 and 2.
- To estimate the change in SF-36 Role Physical scores in subjects ≥ 50 YOA overall, by age, gender and reactogenicity grade and type of symptom (local, systemic) from baseline score to the score on day 7 following both HZ/su vaccinations 1 and 2.
- To estimate the QALY change in subjects ≥ 50 YOA overall, by age, gender, reactogenicity grade and type of symptom (local, systemic) from baseline score to the combined score on days 1 to 7 following both HZ/su vaccinations 1 and 2.
- To assess the impact of reactogenicity on the healthcare resource utilization (i.e., hospitalization, General Practitioners and specialist visits, medication intake) in

subjects ≥ 50 YOA overall, by age, gender reactogenicity grade and type of symptom (local, systemic) following both HZ/su vaccinations 1 and 2.

- To estimate the work loss in subjects ≥ 50 YOA overall, by age, gender, reactogenicity grade and type of symptom (local, systemic) following both HZ/su vaccinations 1 and 2.
- To estimate the work loss for non-dedicated caregivers (e.g., family member) of subjects ≥ 50 YOA overall, by gender, reactogenicity grade and type of symptom (local, systemic) following both HZ/su vaccinations 1 and 2.
- To estimate the extra work for dedicated caregivers of subjects ≥ 50 YOA overall, by gender, reactogenicity grade and type of symptom (local, systemic) following both HZ/su vaccinations 1 and 2.
- To evaluate the safety and reactogenicity following administration of the HZ/su vaccine in subjects ≥ 50 YOA.

Refer to Section 10.2 for the definition of the secondary endpoints.

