#### **3.2. Secondary objectives**

- To estimate the change in the SF-36 PF scale score from baseline score to the mean score over the period day 1 to day 7 following the second HZ/su vaccination in subjects  $\geq 50$  YOA overall.
- To estimate the change in the SF-36 PF scale score in subjects  $\geq 50$  YOA by age, gender and reactogenicity grade and type of symptom (local, systemic) from baseline score to the mean score over the period day 1 to day 7 following both HZ/su vaccinations 1 and 2.
- To estimate the change in SF-36 PF single item scores in subjects  $\geq 50$  YOA overall, by age, gender and reactogenicity grade and type of symptom (local, systemic) from baseline score to the mean score over the period day 1 to day 7 following both HZ/su vaccinations 1 and 2.
- To estimate the change in SF-36 Role Physical scores in subjects  $\geq 50$  YOA overall, by age, gender and reactogenicity grade and type of symptom (local, systemic) from baseline score to the score on day 7 following both HZ/su vaccinations 1 and 2.
- To estimate the QALY change in subjects  $\geq 50$  YOA overall, by age, gender, reactogenicity grade and type of symptom (local, systemic) from baseline score to the combined score on days 1 to 7 following both HZ/su vaccinations 1 and 2.
- To assess the impact of reactogenicity on the healthcare resource utilization (i.e., hospitalization, General Practitioners and specialist visits, medication intake) in subjects  $\geq 50$  YOA overall, by age, gender reactogenicity grade and type of symptom (local, systemic) following both HZ/su vaccinations 1 and 2.
- To estimate the work loss in subjects  $\geq 50$  YOA overall, by age, gender, reactogenicity grade and type of symptom (local, systemic) following both HZ/su vaccinations 1 and 2.
- To estimate the work loss for non-dedicated caregivers (e.g., family member) of subjects  $\geq 50$  YOA overall, by gender, reactogenicity grade and type of symptom (local, systemic) following both HZ/su vaccinations 1 and 2.

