### 4.2. Secondary endpoints

- Change in mean SF-36 PF scale score.
  - Baseline\* versus mean score over the period day 1 to day 7\*\* after second vaccination.
- Change in mean SF-36 PF single item scores.
  - Baseline\* versus mean score over the period day 1 to day 7\*\* after each vaccination.
- Change in SF-36 Role Physical scores.
  - Baseline\* versus score on day 7\*\* after each vaccination.
- Change in the QALY.
  - Baseline\* versus combined score over the period day 1 to day 7\*\* after each vaccination.
- Healthcare resource utilization (i.e., hospitalization, telephone calls, medical visits and specialist visits, medication intake).
  - Days 0 to 6 after each vaccination.
- Work loss for subjects.
  - Days 0 to 6 after each vaccination.
- Work loss for the non-dedicated caregivers.
  - Days 0 to 6 after each vaccination.
- Extra work for dedicated caregivers.

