## 6.2.2. EQ-5D Utility / Quality adjusted life years (QALY)

The calculation of the baseline and post baseline values for the analysis of QALY loss is detailed in section [7.1.3](#).

The 95% CI for Quality-adjusted life year (QALY) mean loss will be obtained using a multiple regression model on the change from baseline EQ-5D utility scores. The model will include age strata, gender and frailty status as the fixed effect.

The 95% CI for utility scores will be obtained pre- and post-vaccination separately assuming that utility scores were normally distributed with unknown variance.

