# Statistical Analysis Plan

Study alias & e-track number(s): ZOSTER-063 (204928)

Each subject will be assigned to one of three categories, Non-Frail, Pre-Frail and Frail.

If the score is  $\leq 3$  then the subject is classified as Non-Frail. If the score is greater than 3 but less than or equal to 8 then the subject is classified as pre-frail. If the score is greater than 8 then the subject is classified as Frail.

A subject must have at least 30 non-missing components in order to be assigned a frailty index classification. However in the event that a subject with a partially completed frailty assessment has a score greater than 8 then the classification will be Frail even if the total number of completed responses is less than 30.

Further details of the Frailty index components can be found in [Appendix A](#)

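### The SAP names no overall mean QALY loss with a CI, and its age and gender LSMEANS weight the frailty classes equally rather than as enrolled

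*SAP*

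**What the plan says.** SAP 3.2 asks for the QALY change "overall, by age, gender, reactogenicity grade and type of symptom (local, systemic) from baseline score to the combined score on days 1 to 7". Protocol 2.2 has the same objective, and SAP 4.2 lists the endpoint after each vaccination.

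SAP 6.2.2 (and Protocol 10.6.2.1) gives the method: "The 95% CI for Quality-adjusted life year (QALY) mean loss will be obtained using a multiple regression model", with age stratum, gender and frailty status as fixed effects. It states no contrast, weights or covariate values at which the mean is taken. SAP 7.1.3.4 narrows this: "The 95% CI for the LSmeans of the QALY loss will be obtained using a multiple regression model". The code there fits "model qaly=agecat frail gender/ cl" and has three LSMEANS statements, for frailty, for gender and for age ("lsmeans agecat/pdiff cl"). It has no ESTIMATE statement and no OM option.

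Protocol 5.2.1 and 5.2.2.2.1 stratify enrolment on age only, in equal thirds. Frailty has three classes with fixed cut-offs (SAP 6.3 and Table 1), and no expected split is given. SAP 6.3 adds: "A subject must have at least 30 non-missing components in order to be assigned a frailty index classification", except that a partial score above 8 is still classed as Frail.

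**The concern.** Followed as written, the code does not report the overall result that the objective puts first. The CL option on the MODEL line concerns the fixed-effect parameters, and the intercept is a reference cell, not an overall mean. The only other CIs described in this part of the SAP are for utility before and after vaccination separately, which are not CIs for the within-subject loss.

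The age and gender levels that are reported refer to a hypothetical population with equal numbers in each frailty class. That is a legitimate adjusted target, but the SAP does not name it. Protocol 1.2.1 and 1.2.2 say the loss from reactogenicity will feed models and be compared with the loss from HZ and PHN. Protocol 1.2.1 also quotes the PHN losses as varying with age. For that use the level of the mean loss and its CI matter, overall and by age, more than contrasts do.

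**Working it through.** **The plan's own figure.** The documents give no precision figure for QALY. The only one is for PF (Protocol 10.3): 1.96 × 21.2/√360 = 2.19, which matches the stated 2.2, and 360/0.9 = 400. That figure is the half-width of a one-sample mean.

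**Weights implied by the code**, if all three frailty classes occur:
- age LSMEANS: 1/3 on each frailty class, 1/2 on each gender
- gender LSMEANS: 1/3 on each frailty class, 1/3 on each age stratum
- frailty LSMEANS: 1/3 on each age stratum, 1/2 on each gender

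Equal age weights match enrolment. Equal frailty weights would match only by coincidence.

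**Level.** Everything from here is assumed, because the documents give no frailty mix, loss by class or SD: n = 380, loss in utility-days per week, frailty independent of age and gender, no age or gender effect. Classes are in the order Non-Frail/Pre-Frail/Frail. The equal-weight mean is the sum of the class losses divided by 3; the enrolled mean is Σ p × loss. For the first row these are (0.15 + 0.30 + 0.60)/3 = 0.35 and 0.60×0.15 + 0.35×0.30 + 0.05×0.60 = 0.225. The last column comes from simulating the additive model (3,000 runs; 1,500 for the 45/40/15 mix).

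| Mix, % | Loss by class | Equal-weight | Enrolled | Age-LSMEAN CIs containing the enrolled mean, SD 0.3 / 0.6 / 1.0 |
|---|---|---|---|---|
| 60/35/5 | 0.15/0.30/0.60 | 0.35 | 0.225 | 5 / 55 / 80% |
| 60/35/5 | 0.20/0.25/0.35 | 0.27 | 0.225 | 77 / 91 / 93% |
| 60/35/5 | 0.30/0.20/0.10 | 0.20 | 0.255 | 63 / 88 / 92% |
| 60/35/5 | 0.25 in all | 0.25 | 0.25 | 95 / 95 / 95% |
| 45/40/15 | 0.15/0.30/0.60 | 0.35 | 0.278 | 27 / 74 / 89% |
| 45/40/15 | 0.20/0.25/0.35 | 0.27 | 0.243 | 86 / 92 / 94% |
| 45/40/15 | 0.30/0.20/0.10 | 0.20 | 0.23 | 81 / 92 / 94% |

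The same CIs cover their own equal-weight target at about 95% throughout. The one-sample overall mean and the unadjusted age and gender means cover the enrolled mean at 94–96% in every scenario.

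**Width.** With balanced age and gender, the variance of an age LSMEAN is about (σ²/n)[3 + Σ(1/3 − p)²/p]; for the unadjusted stratum mean it is 3σ²/n. At 60/35/5 the sum is 0.1185 + 0.0008 + 1.6056 = 1.725. With SD 0.6 the half-widths are 1.966 × 0.6 × √(4.725/380) = 0.132 and 1.979 × 0.6 × √(3/380) = 0.1055. Simulation with flat losses gives 0.134 against 0.105. The wider CI does not need a frailty effect.

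**Frailty rising with age.** Assume 80/19/1, 60/36/4 and 40/50/10% by stratum with losses 0.15/0.30/0.60. The true stratum means are 0.183, 0.222 and 0.270 (for the first, 0.80×0.15 + 0.19×0.30 + 0.01×0.60 = 0.183). The default LSMEANS are about 0.35 in every stratum. The adjusted contrast between the oldest and youngest is therefore about 0, while the enrolled strata differ by 0.270 − 0.183 = 0.087.

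**Can an overall CI be rebuilt?** Yes, for the modelled subjects. The fitted mean at observed covariate shares equals their sample mean, with model-based SE √(residual variance/n). In the age-dependent scenario at SD 0.6, the design matrix and this formula both give 0.03099; the one-sample SE is 0.0316. The rebuilt CI covered the enrolled mean at 93–96%.

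**The case against.** The strongest reply is that the regression is pre-specified in the protocol and promises a CI for mean QALY loss. SAP 7.3 sets decimals for a QALY CI, the table layouts sit in TFL2, and an overall CI can be derived from the printed residual variance. On that view only a line is missing. Most of this stands, and it limits the severity. It does not supply the definition: the SAP does not call for the rebuilt CI, and 6.2.2 leaves open which mean is meant. SAP Table 1 lists age and gender as sub-groups, so unadjusted summaries may already be intended, but the SAP does not say so for QALY loss.

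It also stands that the sizes rest on invented inputs. The 5% coverage needs a fourfold gradient, 5% frail and the smallest SD; the milder and reversed gradients at SD 0.6 or 1.0 give 88–94%.

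A reader might infer more than the documents support:
- That no overall CI can be obtained. It can, as shown above.
- That the LSMEANS are wrong. They are valid for an equal-weight target.
- That the frailty LSMEANS and the PDIFF contrasts describe enrolled subjects. The frailty LSMEANS are equally weighted over age and gender. The contrasts do not depend on the weights, but they are adjusted contrasts, not differences between enrolled stratum means.
- That unclassified subjects might enter as a fourth frailty level. The SAP defines exactly three classes.
- That estimates by reactogenicity grade or symptom type are absent. Table 1 lists both.

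**Conclusion.** The point holds for the SAP text and code. The overall mean QALY loss has no named estimator or CI, and the age and gender levels and CI widths refer to an equal-frailty mix that enrolment does not produce by design. Size and direction cannot be known. The level does not shift if loss does not vary with frailty or if the classes fall in exact thirds, and Protocol 1.2.2 leaves open whether frailty matters. The age CIs are still wider without a shift (0.134 against 0.105 at the assumed 60/35/5% mix and SD 0.6). The endpoint is secondary and Protocol 10.7 keeps the analyses descriptive, so no test is affected. This is a minor point that should be corrected because the repair is cheap and the losses are meant for use in models.

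**What to change.** In SAP 6.2.2 and 7.1.3.4, for each dose:
- Add the overall mean QALY loss with a one-sample t-based 95% CI on all subjects with a QALY value, including those with no frailty class.
- Add unadjusted mean losses with 95% CIs by age stratum and gender (the Table 1 sub-groups), alongside the pre-specified model.
- Keep the model LSMEANS, labelled as adjusted and equally weighted over the levels of the other factors.
- State that subjects with no frailty class drop out of the model.

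The cost is a few lines of text and code and some extra table rows, with no new data. The downside is two sets of age and gender means, which need clear labels so that readers do not confuse them.
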